## Secondary:

- a. To determine the number of patients screened for the study.
- b. To determine the number and proportion of patient screened who met inclusion/exclusion criteria for the study.
- c. To determine the number and proportion of patients enrolled in the study who took more than 80% of prescribed urea doses.
- d. To determine the number and proportion of patients enrolled in the study who thought urea was acceptable.
- e. To determine the patients' average ratings for urea acceptability.
- f. To assess the change in SF-12 (Health Survey) Mental Component Summary (MCS) in patients with chronic hyponatremia due to SIADH from baseline to day 42 of urea therapy.
- g. To assess the change in SF-12 (Health Survey) Physical Component Summary (PCS) in patients with chronic hyponatremia due to SIADH from baseline to day 42 of urea therapy.

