#### Follow-up research assessments:

All patients in group "Urea ON, then Urea OFF" will have scheduled follow up assessments on days 7, 14, and 42 as follows:

- Day 7: Phone interview and basic metabolic panel (BMP).
- Day 14: Phone interview and BMP. More boxes of Ure-Na will be mailed if needed to complete the study.
- Day 42: same assessment as in the baseline study visit

The phone interviews visits will focus on assessing side effects, tolerability, and adherence to urea and as appropriate, dose titration of urea. Side effects and tolerability will be assessed with questionnaires (See Medication Side Effects Questionnaire and Medication Acceptability Questionnaire). Patient also will be asked to bring their study diary to the in-person clinic visits to track their adherence to fluid restriction and urea. Visits at day 0 and day 42 will take place in the Neuromuscular Research Laboratory at the University of Pittsburgh. BMP assessment on days 7, 14 will take place at the UPMC clinical laboratory of patient's choice. At the 42-day visit, patients will be asked to return their study diary and any urea doses they did not consume. During period 1 of the study, patients randomized to group "Urea OFF, then Urea ON" will undergo same assessments as outlined for group "Urea ON, then Urea OFF", although they will not be asked about tolerability or adherence to urea as they will not be on this treatment during this period.

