- A co-investigator will test patients' balance while standing on a specialized piece of equipment. Patient will be asked to stand on both legs on top of a platform in a dynamic moving environment. Patient will go through six conditions, with three trials per condition, lasting about 20 seconds each. Patient will be asked to look forward, and stand as motionless as possible with your arms at your sides. The six conditions include the possibility of moving surroundings or moving base of support. If patient move or lose his/her balance during the procedures, patient will be asked to repeat that part again. Patient will be supported by means of a harness in the equipment to make sure he/she cannot fall over while performing the tests.
- The research coordinator will instruct the patient to restrict his/her fluid intake to no more 1200 mL/day for the next 42 ± 3 days. The research coordinator will provide the patient with a diary to record daily fluid intake.
- Patients will be randomized prior to or at the first study visit (Period 1 Day 0) following completion of baseline assessments. Our biostatistician will generate the randomization list using permuted blocks of random block sizes of 4 and 6 and our systems analyst will load the list into RedCAP. To preserve allocation concealment for consecutively enrolled participants, we will use the randomization module in RedCAP to assign each participant 1:1 to either On-to-Off Urea sequence or Off-to-On Urea sequence.
- If patient is randomized to take On-to-Off Urea sequence then the research coordinator will give the patient 48 urea powder pouches with instructions on how to take the urea every day. The research coordinator will provide the patient with a diary to record patient's daily urea intake.
- This visit will last approximately 2.5 hours.

Second study visit (Day 7 of Period 1)

- The research coordinator will call the patient on the phone to ask some questions about any new symptoms patient might have experienced since his/her last visit.
- The research coordinator will direct the patient to go the UPMC clinical laboratory of the patient's choice that day to have his blood drawn for analysis of a basic metabolic panel.
- If patient is taking urea, we might call the participant on the phone again to ask to change the dose of urea depending on the sodium level results.
- This visit will last approximately 20 minutes.

Third study visit (Day 14 of Period 1)

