- The research coordinator will call the patient on the phone to ask some questions about any new symptoms patient might have experienced since his/her last visit.
- The research coordinator will direct the patient to go the UPMC clinical laboratory of the patient's choice that day to have his blood drawn for analysis of a basic metabolic panel.
- The research coordinator will instruct the patient to bring his fluid and urea intake diaries to the next study visit.
- The research coordinator will give or mail the patient a container with instructions to collect urine for 24 hours prior to next study visit.
- If patient is taking urea then research coordinator will give and/or mail the patient enough urea powder pouches to complete his/her participation in this period of the study.
- If patient is taking urea, we might call the participant on the phone to ask to change the dose of urea depending on the sodium level results.
- If urea dose is adjusted to less than the maximum allowed dose, research coordinator will direct the patient to go the UPMC clinical laboratory of the patient's choice in approximately 7 days to have his/her blood drawn for analysis of a basic metabolic panel.
- This visit will last approximately 30 minutes.

Reminder telephone call

• The research coordinator will call the patient on the phone 48-72 hours before the next study visit to remind him/her of the upcoming study visit.

Fourth study visit (Day 42 of Period 1)

- Patient will come in person to the University of Pittsburgh Neuromuscular Research Laboratory located at [name].
- The research coordinator will collect the patient's fluid and urea intake diaries.
- The research coordinator will ask the patient some questions about any new symptoms patient might have experienced since his/her last visit.
- If patient is taking urea then the research coordinator will ask patient some questions related to acceptability of urea.
- Patient will bring the container with the 24-hour urine collection he/she started the day prior. The research coordinator will send the specimen promptly to the UPMC Presbyterian clinical laboratory for processing and analysis of the following: creatinine, urea nitrogen, uric acid, osmolality, sodium, and potassium

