### 2.3.6. Medication Compliance

Patients will record the doses of urea they consume each day during treatment period in a study diary which will be reviewed during study visits.

We will be assessing patient compliance with urea as described above so patients will not be withdrawn due to non-compliance with the study drug. If patients are noncompliant with serum sodium checks such that the PIs believe the patient should not continue to take urea, we will formally discuss the case with the study team and if it is agreed by all members of the study team that the patient be withdrawn, they will be asked to stop study drug, return remaining doses, and will be formally withdrawn from the study

Subjects withdrawn from the study will be replaced. We will continue recruitment until the target number of patients are enrolled.

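### Acceptability of urea is scheduled only at day 42, so patients withdrawn for persistent symptoms miss it and others who stop may be skipped; the result may be biased upward by an unknown amount

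*Combined protocol and SAP*

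**What the plan says.** **Endpoints.** The synopsis lists acceptability twice among the secondary endpoints: the number and proportion finding the medication acceptable (4) and the average rating (5). Objective d under Secondary in section 1.1 reads "To determine the number and proportion of patients enrolled in the study who thought urea was acceptable". Endpoint 4 refers to patients without saying which ones form the denominator.

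**Visit lists (section 2.2, Research activities).** At the fourth and eighth visits, day 42 of periods 1 and 2: "If patient is taking urea then the research coordinator will ask patient some questions related to acceptability of urea". For the day 7 and day 14 calls the lists say "The research coordinator will call the patient on the phone to ask some questions about any new symptoms patient might have experienced since his/her last" (that is, since the previous contact), and do not mention acceptability. Table 1 has no acceptability row.

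**Follow-up research assessments (section 2.2).** "The phone interviews visits will focus on assessing side effects, tolerability, and adherence to urea"; the next sentence is "Side effects and tolerability will be assessed with questionnaires (See Medication Side Effects Questionnaire and Medication Acceptability Questionnaire". For day 42 this text says "Day 42: same assessment as in the baseline study visit", and the baseline visit has no acceptability item. For the period off urea, patients are assessed in the same way except that "they will not be asked about tolerability or adherence to urea as they will not be on this treatment during this period".

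**Patients who stop.** Section 2.3.6 says "patients will not be withdrawn due to non-compliance with the study drug". Section 10 says that when symptoms persist after a dose reduction, urea is discontinued, the patient returns the remaining doses, the team confers and the patient is formally withdrawn. Data collection then ends and the patient is replaced.

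**The concern.** Patients who give up urea are plausibly those least likely to call it acceptable. If the only scheduled question comes at day 42 and depends on taking urea, the endpoint may describe mainly those who tolerated it. The Summary in section 1.3 names acceptability to ambulatory patients as one of the things the pilot must establish before a larger trial is designed. A figure drawn only from those who persisted could make the next trial's tolerability and retention assumptions too favourable. The plan also has no rule for counting a patient with no acceptability answer: section 2.5.5 on missing data is general and centres on the mixed models for efficacy.

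**Working it through.** **1. Who is asked at day 42**

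| Patient, in the period on urea | Condition read literally | Condition read as on/off-period switch |
|---|---|---|
| Still taking urea | asked | asked |
| Stopped, not withdrawn (2.3.6) | skipped | asked |
| Stopped for persistent symptoms, withdrawn (section 10) | not asked | not asked |

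The third row does not depend on how the condition is read. The second does.

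**2. The plan's nearest figure.** No acceptability rate or precision is given. Section 2.5.1 states a 14% margin for an 80% rate with 30 patients. Using 1.96 × √(p(1−p)/n): 1.96 × √(0.8 × 0.2/30) = 14.3%, which reproduces it. With 24 respondents: 1.96 × √(0.8 × 0.2/24) = 16.0%.

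**3. Proportion, illustrated.** The number unasked and the number of favourable answers are assumptions. The respondent-only rate is x/(30 − s), where s is the number unasked. Over all 30 the rate lies between x/30 (no unasked patient finds urea acceptable) and (x + s)/30 (all do).

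| Unasked, s | Respondents only | All 30, lowest | All 30, highest |
|---|---|---|---|
| 3 | 22/27 = 81.5% | 22/30 = 73.3% | 25/30 = 83.3% |
| 6 | 20/24 = 83.3% | 20/30 = 66.7% | 26/30 = 86.7% |
| 9 | 17/21 = 81.0% | 17/30 = 56.7% | 26/30 = 86.7% |

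With 6 unasked, the respondent-only rate runs from 16.7 points too high (83.3 − 66.7) to 3.3 points too low (83.3 − 86.7). If 5 of the 6 would have said acceptable, the rate over all 30 is 25/30 = 83.3% and the gap is nil. Only near the worst case does the gap exceed the 14-point margin.

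**4. Replacement.** The table holds the total at 30. Suppose instead that 6 patients withdraw after starting urea and are replaced, so 36 start, 30 are asked and 25 find it acceptable. The respondent-only rate is 25/30 = 83.3%. Over everyone who started it is between 25/36 = 69.4% and 31/36 = 86.1%. A denominator of 30 that leaves out the replaced patients is therefore still a respondents-only denominator.

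**5. Average rating.** A mean can use only those who answered. On an assumed 5-point scale, let 24 respondents average 4. If the 6 unasked would average 2, the mean over all is (24 × 4 + 6 × 2)/30 = 3.6; if 3, it is 3.8; if 4, it is 4.0.

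**6. Timing.** The follow-up text names the questionnaire directly after the phone interviews (days 7 and 14), while the visit lists place acceptability at day 42. By section 2.2, a day 7 rating would be made on the 15 g starting dose and a day 42 rating on up to 60 g/day. No section says which rating is the endpoint.

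**The case against.** The strongest reply is that the condition merely separates the two periods, because one visit list serves both sequences. The sentence on the off-urea period supports this. So does the fourth visit, where the same condition governs the return of unused pouches, while the follow-up text asks for unconsumed doses at day 42 without any condition. On that reading a patient who stopped but stayed would be asked. This largely stands as a reading, but the lists use randomized-assignment wording when pouches are dispensed at the first and fifth visits, so a coordinator could apply either meaning. It does nothing for the withdrawn patients.

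Three further points stand:

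- A reader might infer that linking the questionnaire to the phone calls also leaves out those who stop. The opposite is true: asking at days 7 and 14 would capture patients who stop later. The link itself is only by adjacency, and the questionnaires are cited but are not in the text available, so any timing they state cannot be checked.
- A reader might take the 80% in section 2.5.1 to mean that 6 of 30 will have stopped by day 42. It does not. It is a planning figure for dropout and adherence, and section 1.2 measures compliance by doses taken. A patient who misses many doses may still be taking urea at day 42.
- The objective refers to enrolled patients. If unasked patients stay in that denominator and none is counted as accepting, the proportion cannot be inflated. This does not help the average rating, and it silently scores an unasked patient as a negative answer.

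Primary endpoints on doses taken, reasons for non-adherence and adverse events do give some information on those who stop, but they do not replace a rating.

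**Conclusion.** The point holds as a risk of selection, not as a demonstrated bias. Patients withdrawn for persistent symptoms miss the day 42 acceptability questions under any reading. Patients who stop but remain may miss them, depending on how the condition is applied. Upward bias in the average rating is plausible, and in the proportion too if it is computed over respondents only. Both require that those who stop like urea less than those who continue, which is reasonable but not documented. A reader might conclude that the acceptability rate is inflated; the documents do not support that, because they fix neither the denominator nor the number who stop. In the 6-of-30 illustration the error runs from 16.7 points upward to 3.3 points downward. The timing of the questionnaire is inconsistent across sections and needs to be reconciled whatever the size of the bias.

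**What to change.** - At the fourth and eighth visits, ask every patient assigned urea in that period, whether or not still taking it.
- Give the questionnaire at the contact when urea is stopped. For section 10 patients this means before formal withdrawal ends data collection; the return of remaining doses is already a contact.
- Name day 42, or the time of stopping if earlier, as the endpoint rating. Align the follow-up text, the visit lists and Table 1 with it, and label any day 7 or day 14 rating as supplementary.
- Use all patients who started urea, including those later replaced, as the denominator. State that this narrows the enrolled population in objective d to patients who can hold a view.
- Report how many were not rated, with a sensitivity figure counting them as not acceptable.

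The cost is wording plus a short questionnaire for a few more patients at existing contacts. Reported acceptability may be lower. No treatment or withdrawal rule changes.

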#### Table 1 – Study assessments

Baseline (day 0) assessments:

The baseline study visit will take place at the University of Pittsburgh Neuromuscular Research Laboratory. All patients will provide a blood sample to measure a basic metabolic panel, plasma osmolality, and plasma uric acid. The 24h urine collection (started the day before) will be sent for measurement of volume, creatinine, urea nitrogen, uric acid, osmolality, sodium, and potassium. Patients will complete the short form 12 (SF-12) to assess health-related quality of life. They will then undergo assessments of neurocognition and postural control and stability (See Appendix). Specifically, the neurocognition assessment will involve the Perception-Action Coupling Task (PACT), an affordance-based assessment conducted on an iPad, which uses matched pairs of 'virtual' balls and 'virtual' holes to assess patients' ability to accurately assess their action boundaries. Additional neurocognitive testing will involve administration of six measures from the Senaptec Sensory Station™ test battery to examine separate sensorimotor elements including; multiple object tracking, reaction time, perception span, go/no go, depth perception and dynamic visual acuity. Postural control and stability will be determined using both static and dynamic representations of upright stance. Employing non-linear analysis (sample entropy), the complexity and control of the static representation of postural stability in quiet upright stance will be determined. In addition, dynamic postural stability will be assessed using the NeuroCom™ Sensory Organization and Motor Control Tests. These tests enable both the examination of postural control and stability in response to a direct perturbation of the control systems underlying the maintenance of upright posture (vestibular, somatosensory, and visual), giving insight into the relative contributions and/or any deficits in the sensorimotor systems involved in maintaining upright stance in dynamic situations.

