- The research coordinator will draw approximately 14 mL of patient's blood and send the specimen promptly to the UPMC Presbyterian clinical laboratory for processing and analysis of the following: basic metabolic panel, plasma osmolality, and plasma uric acid.
- Patient will complete the SF-12 survey with pen and paper.
- A co-investigator will test patients' reactions and decision making using specialized software on a tablet computer.
- A co-investigator will test patients' balance while standing on a specialized piece of equipment. Patient will be asked to stand on both legs on top of a platform in a dynamic moving environment. Patient will go through six conditions, with three trials per condition, lasting about 20 seconds each. Patient will be asked to look forward, and stand as motionless as possible with your arms at your sides. The six conditions

include the possibility of moving surroundings or moving base of support. If patient move or lose his/her balance during the procedures, patient will be asked to repeat that part again. Patient will be supported by means of a harness in the equipment to make sure he/she cannot fall over while performing the tests.

- The research coordinator will ask patient to stop fluid restriction.
- If patient is taking urea then the research coordinator will instruct the patient to stop taking urea and return all the urea pouches he/she did not use to the research coordinator.
- The research coordinator will provide the patient with a container with instructions to collect urine for 24 hours prior to next study visit.
- This visit will last approximately 2.5 hours.

Reminder telephone call

• The research coordinator will call the patient on the phone 48-72 hours before the next study visit to remind him/her of the upcoming study visit.

Fifth study visit (Day 0 of Period 2)

- Patient will come in person to the University of Pittsburgh Neuromuscular Research Laboratory located at [name].
- Patient will bring the container with the 24-hour urine collection he/she started the day prior. The research coordinator will send the specimen promptly to the UPMC Presbyterian clinical laboratory for processing and analysis of the following: creatinine, urea nitrogen, uric acid, osmolality, sodium, and potassium.

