- The research coordinator will call the patient on the phone to ask some questions about any new symptoms patient might have experienced since his/her last visit.
- The research coordinator will direct the patient to go the UPMC clinical laboratory of the patient's choice that day to have his blood drawn for analysis of a basic metabolic panel.
- The research coordinator will instruct the patient to bring his fluid and urea intake diaries to the next study visit.
- The research coordinator will give or mail the patient a container with instructions to collect urine for 24 hours prior to next study visit.
- If patient is taking urea then research coordinator will give and/or mail the patient enough urea powder pouches to complete his/her participation in this period of the study.
- If patient is taking urea, we might call the participant on the phone to ask to change the dose of urea depending on the sodium level results.
- If urea dose is adjusted to less than the maximum allowed dose, research coordinator will direct the patient to go the UPMC clinical laboratory of the patient's choice in approximately 7 days to have his/her blood drawn for analysis of a basic metabolic panel.
- This visit will last approximately 30 minutes.

Reminder telephone call

• The research coordinator will call the patient on the phone 48-72 hours before the next study visit to remind him/her of the upcoming study visit.

Eighth study visit (Day 42 of Period 2)

- Patient will come in person to the University of Pittsburgh Neuromuscular Research Laboratory located at [name].
- The research coordinator will collect the patient's fluid and urea intake diaries.
- The research coordinator will ask the patient some questions about any new symptoms patient might have experienced since his/her last visit.
- If patient is taking urea then the research coordinator will ask patient some questions related to acceptability of urea.
- Patient will bring the container with the 24-hour urine collection he/she started the day prior. The research coordinator will send the specimen promptly to the UPMC

Presbyterian clinical laboratory for processing and analysis of the following: creatinine, urea nitrogen, uric acid, osmolality, sodium, and potassium.

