- The research coordinator will draw approximately 14 mL of patient's blood and send the specimen promptly to the UPMC Presbyterian clinical laboratory for processing and analysis of the following: basic metabolic panel, plasma osmolality, and plasma uric acid.
- Patient will be given the SF-12 survey to complete with pen and paper.
- A co-investigator will test patients' reactions and decision making using specialized software on a tablet computer.
- A co-investigator will test patients' balance while standing on a specialized piece of equipment. Patient will be asked to stand on both legs on top of a platform in a dynamic moving environment. Patient will go through six conditions, with three trials per condition, lasting about 20 seconds each. Patient will be asked to look forward, and stand as motionless as possible with your arms at your sides. The six conditions include the possibility of moving surroundings or moving base of support. If patient move or lose his/her balance during the procedures, patient will be asked to repeat that part again. Patient will be supported by means of a harness in the equipment to make sure he/she cannot fall over while performing the tests.
- The research coordinator will instruct patient to stop fluid restriction.
- If patient is taking urea then the research coordinator will instruct the patient to stop taking urea and return all the urea pouches he/she did not use to the research coordinator.
- The principal investigator will give the patient the choice to follow up in the UPMC Kidney Clinic to continue the management of his/her hyponatremia.
- This visit will last approximately 2.5 hours.

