## 7.1.2 Risk of Study Procedures

- Blood draws: It may cause pain and bruise. Some people may become light-headed (dizzy) or faint after blood drawing. There is also a rare risk of infection at the site of the blood draw
- Fluid restriction: it may cause thirst.
- Neurocognition assessment: no known risks are associated with this study procedure.
- Posture stability assessment: There is a risk of falling while undertaking the balance testing, and this is heighted with increased age. All participants will use a safety harness during posture stability assessment.
- Collection and storing of PHI and Bio specimens: low risk of breach of confidentiality
- Discontinuing clinically prescribed urea in the hospital: This might cause the blood sodium level to decrease. To minimize this risk, we will first obtain approval from the participant's treating physician in the hospital to make sure is safe to do so and schedule participants for the screening visit within 5-7 days of hospital discharge to ensure a blood sodium level will be checked after urea discontinuation. In addition, we are only enrolling participants with a blood sodium level no lower of 125 mmol/L where the risk of experiencing any symptoms related to low blood sodium is very low.

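### At day 42 the urea acceptability questions, asked only of patients on urea, are listed before the SF-12, so an open-label self-report may be primed differently in the ON and OFF periods

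*Combined protocol and SAP*

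**What the plan says.** In section 2.2, Research activities, the fourth study visit (day 42 of Period 1) and the eighth (day 42 of Period 2) list the same steps in the same order. After the diaries are collected, every patient gets a symptom interview: "The research coordinator will ask the patient some questions about any new symptoms patient might have experienced since his/her last visit". Next comes a conditional item: "If patient is taking urea then the research coordinator will ask patient some questions related to acceptability of urea". The urine container and the blood draw follow, and then the SF-12, worded at visit 4 as "Patient will complete the SF-12 survey with pen and paper" and at visit 8 as "Patient will be given the SF-12 survey to complete with pen and paper". The tablet tests and the balance tests come last.

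The two day-0 visits (first and fifth) list urine, blood draw, SF-12, tablet tests and balance tests, with no symptom or acceptability questions.

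Under Follow-up research assessments, section 2.2 says of patients in their first, untreated period that "they will not be asked about tolerability or adherence to urea as they will not be on this treatment during this period". The difference in questioning is therefore intended. Its position relative to the SF-12 is not discussed.

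Section 2.3.5 states that there is no blinding. Section 2.5.3 calls the SF-12 a secondary exploratory outcome, takes the change from day 0 to day 42 in each period, and fits a mixed model with treatment, period and their interaction.

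**The concern.** The SF-12 is a self-rating of health by patients who know what they are taking. Questions asked just before such a rating can move it, for example by bringing taste or side effects to mind, or by prompting a wish to give a favourable account. If the same questions come first in both conditions, any shift is shared. Here one set is asked in one condition only, so a shift would be read as an effect of urea on quality of life.

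A second, smaller matter concerns secondary objectives f and g in section 1.1. They are worded as the change in SF-12 from baseline to day 42 on urea, which is a within-ON change. Against that yardstick even the symptom interview, which both conditions share, is an imbalance, because it precedes the SF-12 at day 42 and not at day 0.

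**Working it through.** The plan gives no figure on this point to reproduce. The check sets the visit lists side by side and then works out which effects survive in the planned contrast.

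**Step 1: what is listed before the SF-12**

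| Listed step | Day 0 (visits 1, 5) | Day 42, on urea | Day 42, off urea |
|---|---|---|---|
| Symptom questions | no | yes | yes |
| Acceptability questions | no | yes | no |
| Blood draw | yes | yes | yes |

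**Step 2: the contrast**

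Let τ be the true effect of urea on the SF-12, s the effect of the symptom questions, a the effect of the acceptability questions and c the effect of the blood draw. Ignoring period effects:

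- Change in ON = (τ + s_ON + a + c) − c = τ + s_ON + a
- Change in OFF = (s_OFF + c) − c = s_OFF
- ON minus OFF = τ + (s_ON − s_OFF) + a

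The blood draw cancels within each period. The symptom questions cancel if s_ON = s_OFF, leaving τ + a. The acceptability effect does not cancel. The within-ON change is τ + s_ON + a, so there neither question effect cancels.

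**Step 3: can the model recover it?**

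The acceptability questions are asked in Period 1 for the ON-then-OFF sequence and in Period 2 for the OFF-then-ON sequence. They therefore coincide with the treatment indicator for every patient. If a is the same in both periods, the treatment coefficient absorbs all of it, and the period and interaction terms absorb none.

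**Step 4: illustration of size**

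The documents give no value for a. Assume that there is no true effect, that the prompt shifts the ON-minus-OFF difference by b standard deviations of that paired difference, and that a two-sided 5% paired t test is an adequate stand-in for the mixed model. With N patients the noncentrality is b × √N, and √30 = 5.477.

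| Assumed b | Noncentrality, N = 30 | False-positive rate, N = 30 | Same, N = 24 (80% of 30) |
|---|---|---|---|
| 0 | 0 | 5.0% | 5.0% |
| 0.1 | 0.548 | 8.3% | 7.6% |
| 0.2 | 1.095 | 18.5% | 15.6% |
| 0.3 | 1.643 | 35.6% | 29.1% |

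These rates show sensitivity only. Nothing in the documents says that b is this large, or which sign it has.

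**The case against.** **The lists may not be a sequence.** Nothing says that the bullets are binding, and some plainly are not in time order. In the screening list, the call telling patients whether they are eligible comes before the corticotropin test that some of them need to establish eligibility. Section 2.5.6 refers data-collection procedures to a manual that is not part of the documents and may fix the order. This stands: the priming is possible, not documented. It also means that the protocol itself does not protect the SF-12.

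**Patients know their treatment anyway.** They record urea doses daily and, while on urea, are asked about side effects, tolerability and adherence at days 7 and 14. Reordering one visit removes none of that. This stands as a limit on what the change can achieve, but it is no reason to keep an avoidable, treatment-specific prompt next to the questionnaire.

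**Stronger readings that the documents do not support.**

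- A reader might infer that the symptom interview is also unequal between conditions. It is asked of every patient at both day-42 visits, so only the acceptability questions differ.
- A reader might infer that drawing blood before the balance tests compromises the postural endpoints, because section 7.1.2 warns that "Some people may become light-headed (dizzy) or faint after blood drawing" and the baseline description says of the tests that "They will then undergo assessments of neurocognition and postural control and stability". The draw has the same listed position at all four laboratory visits, so an equal effect cancels. The tablet tests come in between, including a seated task lasting 15 minutes (Appendix). A harness is worn during balance testing. No point is made of it here.
- A reader might want to state the bias in SF-12 points. The documents give neither a shift nor an SF-12 standard deviation.

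**Conclusion.** The point holds as a minor, possible bias. If the day-42 lists are followed in order, an ON-only set of questions precedes an open-label self-report, and the planned analysis cannot separate its effect from that of urea. The symptom questions matter for the within-ON change, and matter for ON minus OFF only if their effect differs between conditions.

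The conclusion rests on two assumptions: that staff work through the bullets as listed, and that the questions affect the answers at all. The documents establish neither, and size and direction are unknown. The reach is confined to SF-12 MCS and PCS. The sample size and the primary endpoints are not affected.

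**What to change.** In section 2.2, Research activities, state for visits 1, 4, 5 and 8 that the patient completes the SF-12 first, before any symptom or acceptability questions. Adjust the baseline description under Table 1 to match, since it now mentions the SF-12 after the blood sample. If the manual of procedures sets a visit order, it should say the same.

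Leave the order of the other steps as it is. In particular, keep the symptom questions ahead of the blood draw and the balance tests. If they were moved to the end of the visit, light-headedness from the draw could be reported as a new symptom and blur the attribution of adverse events, which is a primary endpoint.

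The cost is a wording change at four visits and a briefing for the research coordinator. No procedure, visit time or patient is added, and the analysis does not change. The SF-12 would no longer sit between the blood draw and the balance tests, but the tablet tests would, equally at all four visits.
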